#### 3.3 Informed Consent

Legally effective and properly executed written informed consent, in compliance with 21 CFR 50 and the International Conference on Harmonization (ICH) guidelines, will be obtained from each subject before the subject is entered into the trial or before any unusual or non-routine procedure is performed that involves risk to the subject.

Attention will be directed to the basic elements that are required for incorporation into the informed consent under US Federal Regulations for Protection of Human Subjects [21CFR 50.25(a)]. The final IRB-approved document as well as any subsequent approved modified consent document(s) must be provided to NIH/OBA for regulatory purposes. If new information related to the study arises, subjects will be asked to sign a revised document. Signed consent forms will remain in each subject's research chart and be available for the verification by study monitors at any time. Subjects will be given a signed, dated copy of their consent form documents.

#### 3.4 Establish Subject Identification Number

Every research participant will be assigned a Subject Identification code. This will be done prior to any research procedures being scheduled, as they will require a Subject ID.

The Subject Identification code is generated as follows:

- 1) GAL (study identifier)
- 2) The letters DMD (for the DMD gene transfer trial)
- 3) The last two digits represent a sequential number of all candidates being screened

Example: Subject ID: GAL-DMD-01

#### 3.6 Gene Transfer Protocol

#### 3.6.1 Baseline Measures Prior to Vector Injection (Day -45 to Day -1)

Informed consent will be obtained prior to the collection of any data and any study related procedures. Baseline measures from subjects will be obtained prior to gene transfer. A complete physical examination, medical history and concomitant medication history will be obtained. Vitals will be obtained, including temperature, respiratory rate, heart rate, blood pressure, height, and weight. Pre-treatment studies will also include

echocardiogram, ECG, the North Star Ambulatory Assessment (NSAA), a video recorded six minute walk test (6MWT), the 100 meter walk/run test, the maximum voluntary isometric contraction testing (MVICT) of knee extension and knee flexors bilaterally, pulmonary function testing (PFTs) including spirometry, and an open muscle biopsy.

Lab work will include the following:

- Complete blood cell count (CBC) and differential, platelets
- Aspartate aminotransferase (AST)/alanine transaminase (ALT)
- Gamma-glutamyl transpeptidase (GGT)\*
- A Comprehensive Metabolic Panel (CMP) that includes:
  - Albumin/Serum total protein
  - Serum total bilirubin
  - Electrolytes
  - o Calcium
  - Creatinine/Blood Urea Nitrogen (BUN)
  - Serum glucose
  - Alkaline phosphatase
- Prothrombin time (PT)/activated partial thromboplastin time (PTT)
- Amylase
- Creatine kinase (CK)
- Cystatin C
- Antibody testing for Hepatitis B,C and HIV1 and 2.
- Urinalysis
- Whole blood for biobanking
- Urine for biobanking

\* For subjects taking drugs that potentially induce GGT synthesis through the cytochrome P450 system, the clinically significant range will be estimated at two times the levels obtained from the baseline screening test.

Additionally, ELISA will be performed for detection of total antibodies to AAVrh74 and anti-Sda, and ELISpots for T-cell responses to AAVrh74 and GALGT2.

A baseline open muscle biopsy will be performed in one quadriceps muscle. (Note that the rationale and methods of muscle biopsy site selection and performance for this and subsequent biopsies are discussed in Section 3.8)

The baseline evaluation will take place over two visits (one to two weeks apart). Because a preexisting antibody response would be exclusionary, ELISA and ELISpot testing will be performed at the first visit, allowing the results to be reviewed prior to the muscle biopsy with its attendant risks (including sedation). Prescribed and over the counter medications used in the prior two weeks will be recorded at the baseline visit and changes in these medications will be recorded during each subsequent visit. The PI will encourage participants to maintain the medication and supplements they are on at enrollment through the course of the study.

Subjects must already be on prednisone, prednisolone, or deflazacort for at least 12 weeks at time of enrollment as part of the inclusion criteria.

#### 3.6.2 Pre Infusion Visit (Day -1)

Subjects will arrive to the Nationwide Children's Hospital within 24 hours prior to gene transfer. They will undergo a physical exam, a review of concomitant medications and updates to the medical history. Vital signs (heart rate, respiratory rate, temperature, and blood pressure) and weight will be obtained.

- The labs obtained on Day -1 will include:
- Complete blood cell count (CBC) and differential, platelets
- Aspartate aminotransferase (AST)/alanine transaminase (ALT)
- Gamma-glutamyl transpeptidase (GGT)\*
- Prothrombin time (PT)/activated partial thromboplastin time (PTT)
- Creatine kinase (CK)

\* For subjects taking drugs that potentially induce GGT synthesis through the cytochrome P450 system, the clinically significant range will be estimated at two times the levels obtained from the baseline screening test.

An ELISpot for T-cell responses to AAVrh74 and GALGT2 will also be performed.

In previous gene therapy studies at NCH, there has been observed an antigen specific T-cell response to the AAV vectors. This is an expected response between 2 - 4 weeks following gene transfer. One possible consequence to such antigen specific T-cell responses is clearance of the transduced cells and loss of transgene expression. All subjects will already be on prednisone, prednisolone, or deflazacort for 12 weeks at time of enrollment as part of the inclusion criteria. The standard clinical dose of prednisone or prednisolone is 0.75 mg/kg/day, and the standard clinical dose of deflazacort is 0.9 mg/kg/day. In order to dampen the host immune response to our AAV-based therapy, for each subject the glucocorticoid dose will be increased to prednisone or prednisolone 1.0 mg/kg/day, not to exceed 60 mg/day; subjects on deflazacort at enrollment will be placed on prednisone or prednisolone for the immediate peri-injection period. This prednisone dose will be delivered beginning one day prior to the gene transfer and only after passing all inclusion and exclusion criteria (in the event that a measure is repeated on Day -1). This corticosteroid regiment will be continued after gene transfer as discussed in Section 3.7.1, followed by a return to the pre-treatment corticosteroid regimen.

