#### 2.1 Abstract

The proposed clinical trial is a dose escalation study of rAAVrh74.MCK.GALGT2 for DMD patients. There will be a modified intravascular limb infusion(ILI);

 henceforth designated as intravascular limb infusion for gene therapy (ILI-GT) delivered sequentially to the whole each lower limb of DMD subjects via a major lower limb artery.

ILI-GT will be delivered to the muscles of both legs of DMD subjects. This approach to vascular gene transfer builds upon previously published methods used in mice and non-human primates.

Two cohorts will undergo gene transfer in a standard dose escalation scheme to establish maximum tolerated dose (MTD) using toxicity. One subject will be enrolled into the first cohort and one subject will be enrolled in the second cohort. The first cohort will receive the minimally efficacious dose as established by primate studies, consisting of  $2.5 \times 10^{13}$  vg/kg per leg, delivered bilaterally (to total  $5.0 \times 10^{13}$  vg/kg per subject). Once safety is established in the low-dose cohort, the second cohort will receive  $5 \times 10^{13}$  vg/kg per leg, delivered bilaterally (to total  $1.0 \times 10^{14}$  vg/kg per subject).

The baseline open muscle biopsy will be performed in one quadriceps muscle. Open muscle biopsy of the quadriceps (in the leg contralateral to the pre-treatment biopsy) will be performed at 90 days post ILI-GT procedure.

Every effort

will be made to sample these same muscles in all patients; however, in subjects (particularly older ambulant subjects) with limited quadriceps musculature, alternate muscle biopsy sites may be selected at the PIs discretion (including gastrocnemius or tibialis anterior muscles).

The primary objective of this study is the assessment of the safety of intravascular administration of rAAVrh74.MCK.GALGT2 to DMD patients. Safety endpoints will be assessed by changes in hematology, serum chemistry, urinalysis, immunologic response to

rAAVrh74 and GALGT2, and reported history and observations of symptoms. Efficacy measures will be used as secondary outcome for this disorder including a combination of functional 6 minute walk test (6MWT) and direct muscle testing for strength (MVICT) of lower limb muscles.

Subjects will be evaluated at baseline, infusion visit (days 0-2), and return for follow up visits on days 7, 14, 30, 60, 90, and 180 and months 12, 18 and 24.

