#### **Exclusion** Criteria

- 1. Active viral infection based on clinical observations.
- 2. The presence of a DMD mutation without weakness or loss of function
- 3. Subject is amenable to or is currently being treated with eteplirsen.
- 4. Symptoms or signs of cardiomyopathy, including:

- a. Dyspnea on exertion, pedal edema, shortness of breath upon lying flat, or rales at the base of the lungs
- b. Echocardiogram with ejection fraction below 40%
- 5. Serological evidence of HIV infection, or Hepatitis B or C infection
- 6. Diagnosis of (or ongoing treatment for) an autoimmune disease
- 7. Persistent leukopenia or leukocytosis (WBC  $\leq$  3.5 K/µL or  $\geq$  20.0 K/µL) or an absolute neutrophil count < 1.5K/µL
- 8. Concomitant illness or requirement for chronic drug treatment that in the opinion of the PI creates unnecessary risks for gene transfer
- 9. AAVrh74 binding antibody titers  $\geq$  1:50 as determined by ELISA immunoassay
- 10. Presence of circulating anti-Sda antibodies as determined by study approved laboratory.\*
- 11. Abnormal laboratory values in the clinically significant range in the Table 1 below, based upon normal values in the Nationwide Children's Hospital Laboratory:

System	Assay	Normal Range	Abnormal (Clinically Significant)			
Liver Function	GGT	8-80 U/L	> 80 U/L			
Liver Function	Total Bilirubin	0.1-1 mg/dL	$\geq$ 3 mg/dL			
Renal Function	Creatinine	0.3-1.mg/dL	>1.8 mg/dL			
	Platelet Count	140-440x10  platelets/mm 	$\leq$ 90 or $\geq$ 800 x 10  platelets/mm 			
Hematologic	Hemoglobin*	(g/dL) 2 - 6 yrs: 11.5-13.5 6 - 12 yrs: 11.5-15.5 12 - 18 yrs: Male: 13-15 Female: 12-16	For all ages: $\leq 8 \text{ or } \geq 18 \text{ g/dL}$			
	White Blood Cell Count	4 – 6 yrs: 5.5-15.5 6 – 10 yrs: 5-14.5 10 – 21 yrs: 4.5-13.5	For all ages: White blood cell count $\leq 3.5$ or $\geq$ 20 x 10  cells/mL Or Absolute neutrophil count of $\leq 1.5$ x 10  cells/mL			

Table 1 Normal and abnormal laboratory	values at Nationwide Children's Hospital Laboratory
	values at Nationwide Children's Hospital Laboratory

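### The metabolic panel, urinalysis, cystatin C and AAVrh74 antibody have only a Visit 1 value before dosing, so their baseline is about 8 to 45 days old, and no pre-dose recheck of bilirubin or creatinine is scheduled

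*Combined protocol and SAP*

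**What the plan says.** Section 2.1 describes the safety assessment in terms of change: "Safety endpoints will be assessed by changes in hematology, serum chemistry, urinalysis, immunologic response to" the vector and transgene, together with reported history and observed symptoms. One subject is enrolled per cohort.

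Section 3.6.1 sets the baseline window at Day -45 to Day -1 and lists the full laboratory set, including the metabolic panel, amylase, cystatin C, urinalysis and antibody ELISA. On timing it says "The baseline evaluation will take place over two visits (one to two weeks apart". On order it says "ELISA and ELISpot testing will be performed at the first visit, allowing the results to be reviewed prior to the muscle biopsy". Table 2 marks anaesthesia at Visit 2.

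Section 3.6.2 introduces the pre-infusion tests with "The labs obtained on Day -1 will include". The list is blood count with differential and platelets, "Aspartate aminotransferase (AST)/alanine transaminase (ALT"), GGT, PT/PTT and CK. It then adds: "An ELISpot for T-cell responses to AAVrh74 and GALGT2 will also be performed". The same section says the steroid increase starts "only after passing all inclusion and exclusion criteria (in the event that a measure is repeated on Day -1"). It does not say which measures might be repeated.

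Exclusion criterion 11 in section 3.2 covers "Abnormal laboratory values in the clinically significant range in the Table 1 below". Table 1 lists GGT, total bilirubin, creatinine, platelets, hemoglobin and white cell count (with neutrophils).

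**The concern.** Safety is the primary outcome, there is no control group, and each dose is given to one subject. Any reading of a post-infusion laboratory change rests on that subject's own pre-dose value. For the metabolic panel and urinalysis, the first post-infusion value is on Day 1, but the value it is compared with comes from Visit 1. The difference therefore combines whatever happened after screening, the Visit 2 anaesthetic and open biopsy, and the infusion itself. Escalation to the higher dose rests on 30-day data from one subject (sections 3.5 and 4.6), so there is no group average to absorb such noise.

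There is also an eligibility side. Two Table 1 exclusion tests, bilirubin and creatinine, have no scheduled repeat before a single infusion that cannot be withdrawn, while the other four do.

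**Working it through.** The plan gives no figure to reproduce. The check compares the lists in sections 3.6.1, 3.6.2, 3.7.1 and 3.7.2 with the rows of Table 2, followed by date arithmetic.

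**Step 1: which tests have a Day -1 value.** The text and Table 2 agree. The rows for protein/albumin, bilirubin, electrolytes, calcium, creatinine/BUN, glucose, alkaline phosphatase, urinalysis, cystatin C and ELISA are marked at Visit 1 and blank at Visit 2, Day -1 and Day 0. Amylase shows the same pre-dose pattern. Blood count, AST/ALT, GGT, CK and ELISpot are marked at both Visit 1 and Day -1.

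**Step 2: age of the Visit 1 value at infusion (Day 0).**
- Oldest: Visit 1 on Day -45 gives 45 days. Visit 2 then falls 7 to 14 days later, on Day -38 to Day -31.
- Youngest: Visit 2 no later than Day -1, with a gap of at least 7 days, puts Visit 1 at Day -8, so 8 days.
- Range: about 8 to 45 days. The Visit 1 value precedes Visit 2 by 7 to 14 days in every case.

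**Step 3: interval covered by the first post-infusion change.** Interval = age at infusion + nominal day of the first post-infusion sample.

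| Measure | First sample after dosing | As written | With a Day -1 sample |
|---|---|---|---|
| Metabolic panel, urinalysis | Day 1 | 8 + 1 = 9 to 45 + 1 = 46 days | 1 + 1 = 2 days |
| Cystatin C, AAVrh74 ELISA | Day 30 | 8 + 30 = 38 to 45 + 30 = 75 days | 1 + 30 = 31 days |
| Blood count, AST/ALT, GGT, CK | Day 1 | 2 days if Day -1 is taken as baseline | unchanged |

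**Step 4: Table 1 exclusion tests.** GGT, platelets, hemoglobin and white cell count are redrawn on Day -1: 4 of 6. Total bilirubin and creatinine are not: 2 of 6. Adding the metabolic panel on Day -1 makes it 6 of 6.

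**Step 5: which rules use the subject's own baseline.** AST/ALT at 2.5 times baseline (sections 3.7.1.1, 4.5 and 5.6), neutrophils and leukocytes at up to 5000 cells/mm³ above baseline (section 4.5), and, for some subjects, GGT at twice the screening level (footnote in 3.6.2 and elsewhere). All of these analytes are drawn on Day -1. No stated rule uses a subject-specific baseline for the metabolic panel, urinalysis or cystatin C.

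**The case against.** The best case for the plan is that the important analytes are already covered. AST, ALT, GGT and CK are serum chemistry and are drawn on Day -1, so a reader who inferred that no serum chemistry is repeated would be wrong. The T-cell part of the immune response is repeated too; only the antibody ELISA is not. Placing the ELISA at Visit 1 is a reasoned choice, because it spares an ineligible subject the biopsy and sedation.

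A reader might also infer that bilirubin and creatinine are never rechecked. The documents do not support that: section 3.6.2 foresees a criterion measure being repeated on Day -1. What holds is that no repeat is scheduled. Nor is 45 days the age of every baseline; it is the upper end of a range.

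Step 5 shows that no halting or escalation rule turns on the subject's own baseline for these analytes. Halting depends on unanticipated, related events of Grade 3 or higher, and the Table 1 ranges that trigger repeat tests are absolute for bilirubin and creatinine. Those limits also lie well above the normal upper limit of 1 mg/dL (3 for bilirubin, 1.8 for creatinine), and the documents give no estimate of drift or biopsy effect. All of this stands, and it confines the consequence mainly to interpretation and attribution.

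Finally, it would be tempting to say that a Day -1 sample isolates the vector. It does not. The change from Day -1 to Day 1 would still contain the steroid increase that begins on Day -1, the Day 0 anaesthetic and the infusion procedure.

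None of this supplies a pre-dose value close to infusion for the analytes in question. Judging whether an event is possibly related to the study drug is easier with one.

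**Conclusion.** The point holds in a limited form. The metabolic panel, urinalysis, cystatin C and AAVrh74 ELISA have a single scheduled pre-dose value, about 8 to 45 days before infusion and before the Visit 2 anaesthetic and biopsy. Two of the six Table 1 exclusion tests have no scheduled recheck. The text and Table 2 agree, so this is a design weakness and not a contradiction. It changes no stated study decision, but it weakens the only comparator available for part of the primary safety assessment, and the remedy is cheap.

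The range assumes the stated Day -45 to Day -1 window and the stated gap of one to two weeks. A broken footnote to Table 2 suggests that Visit 1 may be spread over several days, and a note allows flexibility for screening visits without giving a window, so the exact ages could differ somewhat. The post-infusion intervals use nominal visit days. Parts of the Day 0 text are missing, but the laboratory rows of Table 2 are legible and blank for that day.

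**What to change.** Add the comprehensive metabolic panel, urinalysis and cystatin C to the Day -1 collection in section 3.6.2 and Table 2. State that, for these analytes only, the Day -1 value is the pre-dose baseline for safety change. State also which repeated measures the parenthesis in section 3.6.2 covers, so that it is clear whether the Day -1 bilirubin and creatinine count toward exclusion criterion 11. Amylase could be added on the same terms.

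Optionally, draw an ELISA sample at the same venepuncture as the baseline for antibody change. Keep the Visit 1 ELISA for eligibility; the Day -1 result may be reported after dosing and so would not serve that purpose.

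Do not let this change move the AST/ALT or GGT reference values used for clinical management. Those analytes are measured twice before dosing. The GGT footnote names the screening test, while sections 3.7.1.1 and 4.5 refer to the subject's baseline without saying which value is meant. These passages should be reconciled separately.

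The cost is a tube or two of blood and a urine sample at a visit where blood is already drawn. The downsides are a small extra blood volume and a possible screen failure on the last day, after the subject has already had the biopsy.

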#### 3.7.1.1 Post-injection immune suppression

All subjects will be discharged from the hospital on oral prednisone or prednisolone at 1 mg/kg/day, which will be adjusted according to IFN-gamma T-cell studies in the following weeks.

If the **30 day** post-infusion IFN-gamma T-cell response shows  $\leq$ 50 SFC per 1 x 10^6 PBMCs, the subject's prednisone or prednisolone dose will be decreased back to the standard clinical dose of 0.75 mg/kg/day. Those subjects who had been on deflazacort may be switched to the standard clinical dose of 0.9 mg/kg day. For either regimen, approximations of these target doses may be allowed to account for pill formulations (for prednisone and deflazacort), as in clinical practice. If either the AST and ALT exceeds >2.5X the subject's baseline values, and results are confirmed on a follow-up blood test, the prednisone or prednisolone regimen will be maintained at 1 mg/kg/day until the enzyme levels fall within a range , 2.5X the baseline value.

If the IFN-gamma T-cell response shows  $\geq$ 50 SFC per 1 x 10^6 PBMCs, we may increase the dose to approximately 2 mg/kg/day depending on T-cell response measured by ELISpot assay, and prolong a subsequent tapering protocol based on the individual subject's immune response profile as assessed by subsequent ELISpot assays (as on the schedule discussed below). Based upon other gene transfer trials performed at NCH, we anticipate that oral prednisone or prednisolone may be administered for up to 120 days post gene transfer prior to return to the standard clinical corticosteroid regimen of each subject.

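### The step-down in Section 3.7.1.1 can leave a boy on a steroid regimen other than his own, and the synopsis lets a Day 90 6MWT result obtained on raised prednisone count as benefit

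*Combined protocol and SAP*

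**What the plan says.** **Where the raised steroid ends.** Section 3.6.2 starts prednisone or prednisolone at 1.0 mg/kg/day on Day -1, "not to exceed 60 mg/day", "followed by a return to the pre-treatment corticosteroid regimen". It adds that "subjects on deflazacort at enrollment will be placed on prednisone or prednisolone for the immediate peri-injection period". Section 3.7.1.1, which holds the operating rules, says that after a low Day 30 T-cell response the prednisone or prednisolone "dose will be decreased back to the standard clinical dose of 0.75 mg/kg/day". It continues: "Those subjects who had been on deflazacort may be switched to the standard clinical dose of 0.9 mg/kg day". Its last sentence speaks of the steroid course "prior to return to the standard clinical corticosteroid regimen of each subject". Approximate doses are allowed to suit pill sizes; a boy's own earlier dose is not mentioned.

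**How long it lasts.** Section 3.7.1.1 anticipates that "oral prednisone or prednisolone may be administered for up to 120 days post gene transfer". After a confirmed AST/ALT rise above 2.5 times baseline, "the prednisone or prednisolone regimen will be maintained at 1 mg/kg/day until the enzyme levels fall within a range" near baseline, and no day limit is given. Table 2 marks the steroid taper through Day 90.

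**Who can enrol.** Inclusion criterion 6 (Section 3.2) asks for at least 12 weeks on a stable dose of prednisone, prednisolone or deflazacort. It sets no dose level.

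**What is judged.** Function is tested at baseline, Days 90 and 180, and Months 12, 18 and 24. The synopsis treats 6MWT stabilization or significant change at Days 90 and 180 as a positive finding; Section 3.11 uses 6 or 12 months.

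**The concern.** Section 2.3.3 says that glucocorticoids improve strength and postpone the loss of walking. There is no control group, so each boy's function is compared with his own baseline. Table 2 places that baseline at screening, and the raised dose begins on Day -1, so baseline reflects his usual regimen. If his steroid dose at a later test is higher or lower than at baseline, the change in 6MWT mixes steroid and gene-transfer effects. With one boy per dose level, nothing in the data can separate the two.

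This can happen in two ways. First, literal use of Section 3.7.1.1 could leave an affected boy on a different regimen at Day 180 and every later visit, including the 6- and 12-month visits used in Section 3.11. Second, Day 90 can fall while the study course is still running, and the synopsis uses Day 90 in its 6MWT rule. Because mere stabilization counts as favorable, a modest steroid effect could be credited to the vector.

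**Working it through.** The plan gives no figure for this point. The check compares the two sections, places the visits against the steroid course, and works out dose ratios.

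**1. Destination of the step-down**

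| | Section 3.6.2 | Section 3.7.1.1 |
|---|---|---|
| Prednisone or prednisolone user | own pre-treatment regimen | fixed 0.75 mg/kg/day |
| Deflazacort user | own pre-treatment regimen | may move to 0.9 mg/kg/day |
| Final wording | own regimen | standard regimen of each subject, which can be read either way |

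The 0.75 step can be read as interim, but Section 3.7.1.1 does not state a second step to the boy's own drug and dose.

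**2. Visits against the course** (windows from Section 3.9)

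- Day 90 ± 7: Days 83 to 97. 120 - 97 = 23, so the whole window lies inside the anticipated 120 days.
- Day 180 ± 14: opens at Day 166. 166 - 120 = 46 days after the anticipated end.
- Of five post-baseline functional visits, one (Day 90) lies within the anticipated course and four lie after it. For those four, the destination of the step-down is the main issue.
- A boy who steps down at Day 30 ± 3 does so by Day 33. 83 - 33 = 50, so he has had at least 50 days at the lower dose when the Day 90 window opens. Day 90 can therefore fall on the raised dose, but need not.

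**3. Raised dose against a standard 0.75 mg/kg/day baseline**

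Ratio = min(1.0 × weight, 60) / (0.75 × weight).

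- Up to 60 kg: 1.0/0.75 = 1.33, or +33%.
- 70 kg: 60/52.5 = 1.14, or +14%.
- 80 kg: 60/60 = 1.00, or 0%.

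The discretionary rise to about 2 mg/kg/day after a strong T-cell response is not used here.

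**4. Fixed 0.75 mg/kg/day against the boy's own prednisone dose**

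The documents give no enrolled doses, so the own doses below are assumptions.

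| Assumed own dose (mg/kg/day) | 0.75 / own dose | Change |
|---|---|---|
| 0.5 | 1.50 | +50% |
| 0.6 | 1.25 | +25% |
| 0.75 | 1.00 | 0% |
| 0.9 | 0.83 | -17% |

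For a deflazacort user on an assumed 0.6 mg/kg/day, a fixed 0.9 would be 0.9/0.6 = 1.50, or +50%; on 0.9 it is no change. A baseline of 1.0 is left out because Section 3.6.2 speaks of increasing each subject's dose to 1.0, which presupposes a lower starting dose.

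These are dose ratios. The documents give no dose-response figure that would turn them into metres walked.

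**The case against.** The best reply is that the destination is already stated. Section 3.6.2 refers to Section 3.7.1 for the interim course and names the pre-treatment regimen as what follows. It limits the deflazacort switch to the days around infusion. Section 3.6.1 encourages subjects to keep their enrollment medication, and the last sentence of Section 3.7.1.1 speaks of each subject's regimen. This largely stands as evidence of intent. A reader might infer a flat contradiction between the sections; the text does not support that. What remains is that the section staff will follow when changing the dose names fixed targets and makes the return to deflazacort optional.

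Four other stronger readings also fail:

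- **That a change of drug alone biases function.** Section 2.3.3 credits both drugs with benefit and ties deflazacort's approval largely to side effects. It reports no strength difference between them, so the concern about function rests on dose.
- **That Day 90 is tested on raised prednisone.** A boy with a low Day 30 response and no confirmed enzyme rise has already stepped down.
- **That 120 days is a limit.** It is an expectation, and the enzyme rule can hold 1 mg/kg/day longer. The 23- and 46-day margins are indicative only.
- **That Day 90 alone makes a positive result.** The synopsis names Days 90 and 180 together, and Section 3.11 does not use Day 90.

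It is also fair to say that medication changes are recorded at each visit and all data go to the DSMB. Printing steroid dose beside each functional result would be a reporting detail. That does not answer the second half of the point, because the synopsis rule itself makes no exception for a result obtained on a raised dose.

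**Conclusion.** The point holds, and it is minor. Section 3.7.1.1, read literally, could move a boy on deflazacort or a stable non-standard dose off his baseline regimen from Day 180 onward. A boy on standard-dose prednisone is unaffected by that wording. Separately, the synopsis rule can credit 6MWT stabilization at Day 90 while the steroid dose is above baseline. That is +33% at 1.0 against 0.75 mg/kg/day up to 60 kg, and less for heavier boys.

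The first part rests on assumed own doses and does not show that either enrolled boy is affected. The second depends on how a boy's immune and enzyme results run. No size of functional bias can be given. Function is exploratory, there are two subjects and safety is the primary outcome, so the consequence is limited to how pre/post functional change is read.

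**What to change.** - **Section 3.7.1.1:** state that, once the immune-driven course ends, each subject returns to his own recorded pre-treatment drug and mg/kg/day dose, former deflazacort users included, allowing for pill size.
- **Synopsis and Section 3.11:** state that a 6MWT result obtained on a steroid dose above baseline, notably Day 90 during the taper, does not count as evidence of gene-transfer benefit. The documents give no conversion between prednisone and deflazacort, so the rule should say how dose is compared for a boy temporarily moved from one to the other.

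The cost is one sentence in Section 3.7.1.1 and one in each place where the 6MWT rule appears. Section 3.6.1 already has medication changes recorded at every visit, so no new data are needed. The downside is that Day 90 function may drop out of the positive-result rule for a boy still on the raised dose.
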